6.4.3.6 Other

Specify any additional analysis that will be done.

6.4.4 Subsets and Covariates

One confounding variable is related to the assumption that the PCR gold standard represents the ground truth, as it has ~5% false positives and 15-30% false negatives. This is the best current standard, but would be improved if combined with a CT scan, but this is not widely done. Thus, it is conceivable the performance of the smell test may be underestimated. Ideally there would be a true ground truth or a PCR assay with higher sensitivity, however this is not currently an option.

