3.2 Purpose of Study/Potential Impact

We posit that most (or even perhaps nearly all) COVID-19+ individuals have a transitory (~7 day) early loss of smell. If this is true and could be robustly and rapidly measured in a device that could be deployed at large scale repeatedly then this could be ultimately used for a massive pre-testing for COVID-19. If this holds true then this olfactory device could outperform PCR tests in the following areas:

Area	PCR	'u-Smell-it' Device
Cost per test	~\$35 (with labor)	<\$1
Time per test	10 min to 5 days	<1 min
Danger to HCW	Considerable for Nasal Swabs (less for saliva)	None; self-performed
Deployment: #/day in USA	~300,000 currently	> ~1-3 million
False Negative Rate	~15-30%	TBD here
False Positive Rate	<5%	TBD here

If the device performs well it ultimately would be broadly deployed as an initial indicator test to identify people likely infected with SARS-CoV-2 that would be confirmed or refuted by secondary PCR screening. It could also serve as a tool to identify local outbreaks of COVID-19.

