6.4.2 Sample Size Considerations

Upon consultation with Yale biostatisticians Profs. [name] and [name], based on our sampling they calculated the following table to shows the precision of sensitivity/specificity measurements for different sample sizes (Table 1). For example, the 95% confidence interval for 90% sensitivity with 100 subjects ranges from 82 to 95% , but if we have 400 subjects, the confidence interval ranges from 87 to 93% (about +/- 3%). Thus the number of participants will be guided by statistical analysis of the data. A minimal estimate is ~100 outpatients that are SARS-Co-V2 positive so as to have good confidence intervals. Here we presume to have at least 100 age/gender matched SARS-Co-V2 negative subjects. If there are 3:1 SARS-Co-V2 negative to SARS-Co-V2 positive then ~400 outpatients (300 +100) will be tested. For the more exploratory testing with asymptomatics we will limit the study to up to 250 HCW. If the results are encouraging with a loss of smell in asymptomatic the sample size could be increased to increase the precision, as done in the outpatient cohort.

Table 1 (replicated from before): Sample Size Calculations (Width of a 95% confidence interval around the proportion).

*Denominator is those that are COVID+ for sensitivity and those that are COVID- for specificity

Sens/Spec	Sample Size for Denominator*						
	100	150	200	250	300	350	400
0.50	0.20	0.17	0.14	0.13	0.12	0.11	0.10
0.60	0.20	0.16	0.14	0.13	0.11	0.11	0.10
0.70	0.19	0.15	0.13	0.12	0.11	0.10	0.09
0.80	0.17	0.13	0.12	0.10	0.09	0.09	0.08
0.90	0.13	0.10	0.09	0.08	0.07	0.07	0.06

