6.4.3 Planned Analysis

6.4.3.1 Primary Analyses

Loss of smell in outpatients will be compared to the presence of SARS-CoV-2 coronavirus, as determined by RT-PCR. Key metrics that will be statically evaluated and done with support of YCCI and Yale biostatisticians Profs. [name] and/or [name] Sensitivity are:

- Sensitivity
- Specificity
- Accuracy
- Repeatability

- Other parameters that will be considered are the Area under the Curve (AUC)

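### PCR is analysed as the truth although the plan states its error rates, so the confidence intervals describe agreement with PCR and can exclude the device's accuracy for infection

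*Combined protocol and SAP*

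**What the plan says.** Section 6.4.3.1 sets the primary comparison: "Loss of smell in outpatients will be compared to the presence of SARS-CoV-2 coronavirus, as determined by RT-PCR". Section 6.4.3.2 uses the same reference for the asymptomatic cohort. The footnote to Table 1 in section 6.4.2 defines the denominators: "Denominator is those that are COVID+ for sensitivity and those that are COVID- for specificity". The precision example there is that "the 95% confidence interval for 90% sensitivity with 100 subjects ranges from 82 to 95" percent.

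Section 6.4.4 raises the reference problem itself. It says of PCR that "it has ~5% false positives and 15-30% false negatives", calls it the best standard now available, and adds that "it is conceivable the performance of the smell test may be underestimated". It specifies no analysis. Section 6.4.3.6, reserved for other analyses, is unfilled template text.

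Section 3.2 says that, if the hypothesis holds, "this olfactory device could outperform PCR tests in the following areas". Its table includes false-negative and false-positive rates. The false-negative rate for PCR agrees with section 6.4.4, but the false-positive row reads "False Positive Rate <5% TBD here", an upper bound where section 6.4.4 has an approximate value.

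**The concern.** The Table 1 intervals carry binomial sampling error only. When the reference misclassifies patients, the apparent sensitivity and specificity move away from the values for infection, and no increase in sample size removes that shift. The plan states the size of the reference error but leaves the reader to guess its effect.

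The results are meant to be read as accuracy for infection. Section 6.1.1 makes an emergency authorisation request depend on performance, sensitivity above all. Section 6.4.3.5 uses sensitivity to project cases found and missed at national scale. Section 3.2 sets the device's error rates beside PCR's, yet the device's rates are measured against PCR: every PCR error on which the device is right counts as a device error.

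Section 6.4.4 also names only one direction of bias. That direction follows if the two tests err independently given infection status. The plan does not state or defend that condition.

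**Working it through.** **Inputs from the documents.** PCR false-positive rate f about 5% (6.4.4) or below 5% (3.2), read as 1 - specificity. PCR false-negative rate g = 15-30%. PCR-positive share r = 100/400 = 25%, from the 3:1 example in 6.4.2. Sensitivity denominator 100; specificity denominator 300.

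**Assumed, because the documents give no value.** Device true sensitivity 0.90 and specificity 0.95 for infection. Errors are independent at first.

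**Step 1: the plan's own figure.** Exact (Clopper-Pearson) 95% limits for 90/100 are 0.824-0.951 and for 360/400 are 0.866-0.928. These are the stated 82-95% and 87-93%. The same method matches 34 of the 35 cells of Table 1; the exception, 0.60 at n=250, is 0.1248 against a printed 0.13. Table 1 is sound as sampling error.

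**Step 2: formulas.**
- Infected share: p = (r - f)/(1 - g - f)
- Infected among PCR-positives: PPV = p(1 - g)/r
- Uninfected among PCR-negatives: NPV = (1 - p)(1 - f)/(1 - r)
- Apparent sensitivity = PPV × 0.90 + (1 - PPV) × 0.05
- Apparent specificity = NPV × 0.95 + (1 - NPV) × 0.10

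**Step 3: results at r = 25%.**

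| f | g | p | PPV | NPV | Apparent sensitivity (95% CI, n=100) | Apparent specificity (95% CI, n=300) |
|---|---|---|---|---|---|---|
| 5% | 15% | 0.250 | 0.850 | 0.950 | 0.773 (0.675-0.848) | 0.908 (0.868-0.937) |
| 5% | 30% | 0.308 | 0.862 | 0.877 | 0.782 (0.686-0.857) | 0.845 (0.801-0.886) |
| 0% | 15% | 0.294 | 1.000 | 0.941 | 0.900 (0.824-0.951) | 0.900 (0.860-0.932) |
| 0% | 30% | 0.357 | 1.000 | 0.857 | 0.900 (0.824-0.951) | 0.829 (0.783-0.871) |

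Intervals use the nearest whole counts (77, 78 and 90 of 100; 272, 254, 270 and 249 of 300). At f = 5%, both sensitivity intervals exclude 0.90. All four specificity intervals exclude 0.95. A perfect device at f = 5% would read PPV and NPV, that is 85-86% and 88-95%.

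Between the two extremes, sensitivity reads about 0.88 at f = 1% and 0.85-0.86 at f = 2%. If only 100 matched negatives enter, the specificity interval at f = 5% and g = 15% (91/100) is 0.836-0.958 and contains 0.95. At g = 30% (85/100) it is 0.765-0.914 and does not.

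**Step 4: direction.** Let the device detect 0.90 of PCR-detected infections and b of PCR-missed infections. True sensitivity is (1 - g) × 0.90 + g × b. Apparent sensitivity does not involve b, so it stays as in step 3.
- f = 5%, g = 30%: true = 0.63 + 0.30b against apparent 0.782. Overestimation needs b below (0.782 - 0.63)/0.30 = 0.51.
- f = 5%, g = 15%: true = 0.765 + 0.15b against apparent 0.7725. Overestimation needs b below 0.0075/0.15 = 0.05.
- f = 0%: apparent is 0.90, so any b below 0.90 gives overestimation.

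The sign therefore depends on f, g and b together, and the documents give no value for b.

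**The case against.** The strongest reply is that the plan discloses the problem, quantifies it, and notes that no better truth is available. Its wording is hedged and points the right way under independence. The primary objective (4.2) defines infected subjects as those identified by PCR, and against that target the intervals are valid. Section 6.3 also records CT or serology where given, takes inconclusive PCR results out of the main analysis, and considers re-testing some patients who fail the smell test but are PCR-negative. Section 7.6 offers a state laboratory for secondary testing.

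Much of this stands. None of it corrects an estimate, though. The re-testing is optional, covers only one of the two discordant groups, and has no rule for how its result enters the analysis.

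Four stronger readings are tempting, and the documents do not support them:
- *The intervals miss the truth by more than their width.* At the 3:1 ratio with f = 5%, the sensitivity shift is 0.12-0.13, which does not exceed the stated 0.13 width, and it vanishes at f = 0%. The specificity shift exceeds the n=300 interval width at g = 30% (0.105 against 0.085 at f = 5%), but the upper limit still lies only 0.064 below 0.95.
- *The plan claims the device can only be underestimated.* Section 6.4.4 says that this is conceivable, no more.
- *Overestimation is shown.* With b assumed at 0.20-0.40 and g = 30%, a true sensitivity of 69-75% reads 78%. The interval for 78/100, 69-86% (lower limit 0.686), still contains those values.
- *Most PCR-positive asymptomatic subjects are uninfected.* A PPV of 42-47% needs an assumed 5% infected and f = 5%. At f = 1% it is 79-82%; at 20% infected with f = 5% it is 78-81%. The documents give no prevalence for this cohort.

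**Conclusion.** The concern holds as a gap in the analysis plan. PCR is treated as truth, the plan's own error rates are used nowhere, and the intervals can exclude the device's accuracy for infection. For an assumed 90%/95% device with independent errors, 25% PCR-positive and 5% false positives, sensitivity is understated by 12-13 points and specificity by 4-11.

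The sensitivity result rests on the false-positive rate. An approximate 5% and an upper bound of 5% are not contradictory, but across 0-5% the sensitivity bias runs from none to 13 points, so sections 3.2 and 6.4.4 need one agreed range. Specificity is affected throughout that range and still reads 83-90% at 0%. Underestimation is the expected direction under independence. Overestimation remains possible under positive dependence and cannot be sized from the documents.

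**What to change.** - In 6.4.3.1 and 6.4.4, pre-specify a bias analysis that recomputes sensitivity and specificity, with intervals, over PCR false-positive rates of 0-5% and false-negative rates of 15-30%. Do this under independence and under a stated range of positive dependence, separately for each cohort. Take the PCR-positive share from all tested subjects before age and gender matching, because matching alters it.
- Report the main results as positive and negative agreement with PCR, and say in 6.4.4 that bias may go in either direction.
- Reconcile the false-positive rate between 3.2 and 6.4.4.
- State beside the 3.2 table that error rates measured against PCR cannot show that the device outperforms PCR on false negatives or false positives.

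The cost is a short calculation on the existing 2×2 tables and some rewording. No new data are needed. The downside is a wider reported range.

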6.4.5 Handling of Missing Data

Tests with missing data of the olfactory performance will be excluded.

7 Trial Administration

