6.3 Study Procedures

For the outpatient drive-up studies the following protocol steps will be performed.

1. As patients drive-up and are still in the car with the windows closed a HCW with suitable PPE will place a ziplock pouch under the wiper of the driver's side windshield. The bag will contain the following materials:
 - a. A consent form
 - b. A pre-sharpened 'golf-pencil'
 - c. The 'u-Smell-it' olfactory device test card
 - d. A multiple choice answer form
2. While in the car, if the patient consents, they will sign the consent form, read the simple instructions (which are also shown as pictograms to make it very easy to follow), take the test, and fill in the answers. This process will take about 1 minute.
 - a. Description of the test: The test card device has 5 windows each printed with a different scent (or no scent) and marked #1, 2, 3, 4, and 5. The test subject merely needs to use their pencil to scratch back and forth 3 times the first window, sniff the window, and looking at the answer score sheet pick the best choice of five choices and fill in the multiple choice circle ("no scent", and scent A, B, C or D). For instance this could be: no scent / apple / orange /

cherry /banana / rose. This procedure will be repeated for each of the 5 windows.

- b. The subject will also be asked on the test if:
 - i. "Do you have any new loss of taste or smell?" (Yes/No)
 - ii. "Does anything smell different in the last year?" (Yes/No)
 - iii. Do you have a stuffy or runny nose? (Yes/No)
- c. If the test site is not part of EPIC the patient will be asked their gender and age band (18-29, 30-39, 40-49, 50-59, 60-69, 70-79, 80+)

3. After the patient completes the test they will pull out the **Consent and Multiple choice questionnaire form**, and with the window still CLOSED hold it up to the driver's side window and it will then be photographed by the attending HCW (likely an ENT resident doctor) whom will add the unique identifier number and add it to the EPIC system.

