 - a. [Alternative should there be any issues with the camera or the patient must get out of the car]: The patient will take the completed test packet, place it back in the pouch and under the windshield. The HCW will take the packet and remove the **Consent Form** and **Multiple choice questionnaire form**, check if it is completed (if ask the patient), and place all remaining materials in a biohazard box for destruction. The Consent form and the Questionnaire will be digitalized (scan or photographed) and linked with EPIC so as to be compared to the PCR test results.
4. Information from the uploaded and **Multiple choice questionnaire form** will be entered by a person authorized to access the information into a table that includes:
 - a. Unique identifier
 - b. Gender
 - c. Age band (10 year)
 - d. Y/N to patient self-identified new loss of smell or taste
 - e. Y/N to patient response to "things in the last year smell different"
 - f. Y/N to patient self-identified blocked or stuff nose
 - g. Individual answers on the 5 window smell test
 - h. RT-PCR results for SARS-CoV-2 (+, - or Inconclusive)
 - i. Any other tests for COVID19 (CT or Serological) if given
5. The data will be analyzed in the following fashion:
 - a. Patients that report a blocked or stuffy nose will be excluded from the main analysis (as COVID-19 loss of smell is not due to nasal congestion); but will be analyzed separately to see how this would confound any interpretation.
 - b. Patients that are denoted SARS-CoV-2 "inconclusive" will be excluded from the main analysis; but will be separately analyzed to see if they colocalize with normosmia or anosmia.
 - c. Patients will be split into SARS-CoV-2 positive and negative. As the negative pool is likely to be much larger it will be statistically matched by gender and age profile (potentially with larger bands – e.g. 20 year, depending on the sample size)

- d. The + and - SARS-CoV-2 groups individual performance on the smell test (score 0-5) will be plotted as a histogram. A cutoff will best be chosen to segregate people with normosmia and anosmia (e.g. score = 2 or 3).
- e. False Positives (FP) and False Negatives (FN) will be identified and used to measure the selectivity and sensitivity, respectfully.
- f. Based on the statistical performance (see Table 1) we will determine when we have enough patients to complete the study with a given value of precision.

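### Read plainly, the missing-data rule drops a smell test for one blank window, even when that blank cannot change the pass/fail result, and nothing in the plan would reveal selective loss

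*Combined protocol and SAP*

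**What the plan says.** Section 6.4.5 is the whole missing-data provision: "Tests with missing data of the olfactory performance will be excluded". It sets no threshold for how much must be missing and no scoring rule for a blank. It asks for no count of exclusions by PCR result and no sensitivity analysis.

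The rest comes from section 6.3:
- **The test.** Each card has five windows, with five answer choices per window, one of them for no scent: "This procedure will be repeated for each of the 5 windows".
- **Main collection route (step 3).** The subject holds the form to the closed car window and "it will then be photographed by the attending HCW". No completeness check is stated.
- **Fallback route (step 3a).** When the packet is handed back, staff are to "check if it is completed (if ask the patient".
- **Data recorded (step 4g).** "Individual answers on the 5 window smell test", so partial tests can be identified and rescored.
- **Use of the score (step 5d).** "individual performance on the smell test (score 0-5) will be plotted as a histogram" by PCR group, and then: "A cutoff will best be chosen to segregate people with normosmia and anosmia (e.g. score = 2 or 3". Section 6.4.3.1 adds that the AUC will be considered.

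**The concern.** Sensitivity and specificity are primary outcomes, and section 6.1.1 ties the plan to seek emergency authorization to high performance, sensitivity above all. Dropping incomplete tests raises two problems.

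First, some of the dropped tests have a known result. A subject with four correct answers and one blank passes at either example cutoff, whatever the blank would have been.

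Second, if blanks are related to smell, exclusion is selective. A failed smell test is the positive result here. If failing tests are dropped more often than passing ones, true positives leave the sensitivity calculation and false positives leave the specificity calculation. Sensitivity is then understated and specificity overstated. Without a count of exclusions by PCR result, a reader of the results could not tell whether this had happened.

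**Working it through.** **1. The plan's own precision figure.** Section 6.4.2 gives a 95% CI of 82 to 95% for 90% sensitivity with 100 subjects. The exact (Clopper-Pearson) interval for 90/100 is 82.4 to 95.1%, width 0.127, so the figure reproduces (Table 1 prints 0.13).

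**2. Which partial tests are already settled.** Let a pass be a score of at least *c*, with *k* correct answers and *b* blanks. The final score lies between *k* and *k + b*. The result is settled as a pass if *k* ≥ *c*, and as a fail if *k + b* < *c*.

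| Blanks | Possible *k* | *c* = 2 | *c* = 3 |
|---|---|---|---|
| 1 | 0 to 4 | open only at *k* = 1; 4 of 5 settled | open only at *k* = 2; 4 of 5 settled |
| 2 | 0 to 3 | settled at 2, 3; 2 of 4 | settled at 0, 3; 2 of 4 |
| 3 | 0 to 2 | settled at 2 only | none settled |
| 4 | 0 to 1 | none settled | none settled |

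A wholly blank form is never settled. If the cutoff is instead read as the highest failing score, so that 3 means a pass needs 4, one blank still leaves 4 of 5 counts settled (open only at *k* = 3).

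These are counts of patterns, not probabilities. Assume an independent chance of a correct answer per window of 0.2, 0.5, 0.8 or 0.9. The share of one-blank tests that is settled is then 59 to 99.6% at *c* = 2 and 62.5 to 95% at *c* = 3.

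**3. Size of bias if blanks depend on the result.** The documents give no blank rate and no expected sensitivity or specificity, so all inputs here are assumed: true sensitivity *s* = 0.80, true specificity *p* = 0.90, a share *a* = 0.02 of passing subjects with a blank, and a share *f* of failing subjects with a blank, the same in both PCR groups.

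- Observed sensitivity = *s*(1−*f*) / [*s*(1−*f*) + (1−*s*)(1−*a*)]
- Observed specificity = *p*(1−*a*) / [*p*(1−*a*) + (1−*p*)(1−*f*)]

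| *f* | Sensitivity | Specificity |
|---|---|---|
| 0.05 | 0.760/(0.760+0.196) = 79.5% | 0.882/(0.882+0.095) = 90.3% |
| 0.15 | 0.680/(0.680+0.196) = 77.6% | 0.882/(0.882+0.085) = 91.2% |
| 0.25 | 0.600/(0.600+0.196) = 75.4% | 0.882/(0.882+0.075) = 92.2% |

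If *f* = *a*, both formulas return the true values and there is no bias. The effect also depends on the true sensitivity. With *a* = 0 and *f* = 0.20, 0.90 reads 0.72/(0.72+0.10) = 0.878, and 0.70 reads 0.56/(0.56+0.30) = 0.651.

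For scale, Table 1 gives an interval width of 0.17 at 80% with 100 positives and 0.08 with 400. A 4.6-point shift is well inside the half-width of the first (8.5 points) but exceeds that of the second (4 points).

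**4. Loss of numbers if blanks are unrelated to smell.** This is a separate scenario and must not be added to step 3. With a blank rate *r* per window, the share dropped is 1 − (1−*r*)^5: 4.9% at *r* = 1%, 9.6% at 2%, 22.6% at 5%. Losing 10 of 100 positives widens the exact interval at 90% sensitivity from 0.127 to 0.135. Keeping 100 would need 100/0.9 = 111.1, so 112.

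**The case against.** The strongest reply is that the mechanism is unproven. A reader might infer that the rule deletes people who left windows blank because they smelled nothing. The documents do not support that. The form gives such a person an answer to mark, and nothing reports that anyone leaves blanks instead. The larger shifts in step 3 need failing subjects to leave blanks 7.5 to 12.5 times as often as passing ones; at 5% against 2% the effect is negligible. This stands, so the bias can be stated only as conditional.

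A reader might also infer that the study would fall short of its roughly 100 positives. That does not follow. Section 6.4.2 calls 100 a minimal estimate, and section 6.3 step 5f lets the precision reached decide when enrolment is sufficient. Lost positives can be replaced, and a random 10% loss costs little precision anyway.

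Three further points stand in part. The rule could be meant only for forms with no usable score, but it does not say so. A test is settled only once the cutoff is fixed, and here the cutoff is chosen from the data; a partial test has no exact place in the histogram or the AUC. Step 3 does not rule out a completeness check, and staff do handle each record when they photograph it.

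The obvious remedy, scoring every blank as a failure in the main analysis, is open to challenge too. It builds in the unproven mechanism and can turn open results into fails: one correct answer with four blanks would count as smell loss at a pass mark of 2 or 3.

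None of this defends discarding a result that is already determined, or leaving exclusions uncounted by PCR result.

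**Conclusion.** The concern holds in limited form. On its plain reading, section 6.4.5 removes a subject for one blank window although, once a cutoff is set, most one-blank patterns (4 of 5) already determine the result. That part is arithmetic and needs no assumption about why windows are blank. The main route also lacks the completeness check that the fallback has.

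Bias is possible but not demonstrated. Its direction, if blanks are commoner among failing subjects, is sensitivity down and specificity up. Its size rests wholly on assumed rates: from about 0.5 points of sensitivity and 0.3 of specificity (5% against 2%) to about 5 and 2 points (25% against 2%), at true values of 80% and 90%. The plan as written would not let anyone see where in that range the study lies. This is a modest weakness, worth correcting because correction is nearly free.

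**What to change.** 1. Apply the step 3a completeness check in the main route, before the photograph is accepted.
2. Replace section 6.4.5: a partial test is kept and classified at the chosen cutoff whenever its lowest possible score (blanks wrong) and highest possible score (blanks right) give the same result. State which tests were used to choose the cutoff.
3. Report the number of incomplete tests, including wholly blank forms, by PCR result.
4. Report sensitivity, specificity and AUC with all blanks scored incorrect and with all blanks scored correct, alongside complete tests only, holding the cutoff fixed. This is needed because rule 2 still leaves open tests unclassified. At a fixed cutoff the two scorings bound sensitivity and specificity; for the AUC they are two scenarios, not bounds.

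A blank should not be coded as a no-scent answer. Section 6.3 step 2a allows a window to be truly unscented, so that coding could earn a point.

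The cost is a brief check per form, a few sentences in 6.3 and 6.4.5, and a few extra table rows. No new data are needed, because window-level answers are already recorded.
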